**Sample size calculation:** Since no previous study has evaluated an acupuncture-based intervention in older adults with delirium, a pilot study of 32 patients [acupuncture group (n=24); control group (n=8)] was designed to estimate accurately the sample size for our current study. In the pilot study, delirium-free days were  $3.2 \pm 1.6$  in the acupuncture group as compared with  $1.7 \pm 2.4$  in the control group. Taking into account a Type I error (alpha) of 0.05, a power of 0.80, pairwise comparison between our two study arms, and using G\*Power 3.1.9.4 software, we calculated a minimal sample size of 28 patients in each of the 2 study arms.

**Randomization:** Patients were randomized in two groups by convenience allocation according to acupuncturists' working days: patients with delirium diagnosed on Sunday, Monday, Wednesday or Thursday were assigned to the acupuncture arm, while patients with delirium diagnosed on Tuesday, Friday or Saturday were assigned to SOC arm. Blinding was clearly not feasible.

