**Statistical methods:** Demographic and clinical data was analyzed at baseline to measure the balance among the study groups. Quantitative variables were described using mean and standard deviation or median with range (minimum and maximum) depending on their distribution. Qualitative variables were described using frequency and percentage distributions. Next, we showed that our variables distribute equally between the two groups. For comparing normally distributed variables between our study groups, we used the t-test for independent samples. For comparing variables that do not distribute normally between our study groups, we used the Mann-Whitney test. For comparing qualitative variables between our study groups, we used the independent Chi-square test and Fisher exact test. Time-to-first delirium remission was evaluated using the Kaplan-Meier product limit survival estimator with log-rank between-group comparison and Cox regression was performed for multivariate adjustment of potential confounders. Hazard ratio (HR) with confidence intervals (CI) was calculated for each independent variable and controlled for all other independent variables in the regression. Patients who died or were discharged before day 7 had all subsequent days counted as the last day of evaluation in terms of both CAM and CAM-S. Intention-to-treat (ITT) analysis was planned to provide more information on the effect of the intervention. We explored the variables for possible collinearities, interaction, and confounders. All comparisons were two-sided with

significance level set at  $p<0.05$ . Data analysis was performed using IBM SPSS version 22 statistics software.

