## **RESULTS:**

Baseline patient data: Overall, 132 patients were screened for eligibility. Among them, 81 were recruited – 50 to the acupuncture arm and 31 to the SOC arm. Baseline sociodemographic and medical characteristics were similar in the two study arms as shown in Table 1. To note, all the patients randomized to the acupuncture arm were treated with acupuncture, while no patient assigned to the SOC arm received acupuncture (Fig. 1), so the planned ITT analysis was not required. In the acupuncture arm, 14 (28%) were censored (dead/discharged in the 7 days of follow-up), as compared with 8 (26%) in the SOC arm ( $p=0.87$ ). No difference in the baseline characteristics was noted between censored patients and patients completing the 7 days of follow-up.

Primary endpoint: Time-to-first delirium remission was shorter in the acupuncture arm as compared to the SOC arm ( $p<0.001$  for log-rank comparison, Fig. 2A). In the 7 days of evaluation, we calculated a number needed to treat (NNT) of 3 for first delirium remission. A multivariate Cox regression analysis was also conducted to evaluate the association of study arm allocation with the primary outcome (time-to-first delirium remission), adjusted for potential sociodemographic and medical confounders (age, gender, APACHE-II score, Charlson comorbidity index, number of psychotropic drugs, mobilization, cognitive impairment, reason for admission and type of delirium). The analysis showed that after adjusting for potential confounders, the time-to-first remission of delirium in the acupuncture arm was significantly shorter than in the SOC arm [HR 0.267 (95% CI 0.098-0.726,  $p=0.010$ ), Fig. 2B], while HR of potential confounders were not statistically significant. This means that acupuncture associated with SOC significantly increased the incidence of delirium remission by about 4-times, as compared to SOC only, after adjusting for sociodemographic and medical characteristics (model significance:  $p=0.042$ ). Furthermore, in the 7 days of evaluation, a significantly higher number of delirium-free days was found in the acupuncture arm [median 5.5 (0-6)] as compared with the SOC arm [median 0 (0-6)],  $p<0.001$ . Based on these results, the power of the study was calculated as 100%.

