## Tables and figures:

[figure not shown]
Table 1: Baseline characteristics

Baseline characteristics		Acupuncture + SOC (n=50)	SOC only (n=31)	p
Male gender – N (%)		25 (50%)	19 (61%)	0.36
Age (years) – Mean (SD)		84.0 (7.8)	85.3 (6.7)	0.45
Prevalent delirium – N (%)		26 (52%)	16 (52%)	1.00
APACHE-II – Median (min-max)		9 (5-22)	11 (6-19)	0.31
Number of medications – Median (min-max)		8 (0-16)	9 (1-15)	0.38
Number of psychotropic drugs – Median (min-max)		1 (0-5)	1 (0-3)	0.66
Mobilization – N (%)	Normal	24 (48%)	9 (19%)	0.19
	Walking aid	15 (30%)	15 (48%)	
	Wheelchair	2 (4%)	3 (10%)	
	Bedridden	9 (18%)	4 (13%)	
IQCODE – N (%)	Normal cognitive status	28 (56%)	12 (39%)	0.35
	Mild dementia	17 (34%)	16 (52%)	
	Moderate dementia	4 (8%)	3 (10%)	
	Severe dementia	1 (2%)	0	
ADL – Median (min-max)		4.5 (0-6)	4 (0-6)	0.36
Reason for admission – N (%)	Infection	19 (38%)	12 (39%)	0.94
	Dyspnea	9 (18%)	9 (29%)	
	General Deterioration	8 (16%)	4 (13%)	
	Falls	3 (6%)	3 (10%)	
	Anemia	2 (4%)	1 (3%)	
	Other	9 (18%)	2 (6%)	
Delirium category – N (%)	Hyperactive	23 (46%)	12 (39%)	0.45
	Hypoactive	15 (30%)	12 (39%)	
	Mixed	9 (18%)	3 (10%)	
	Subsyndromal	3 (6%)	4 (13%)	
Hearing and/or visual impairment – N (%)		26 (52%)	22 (71%)	0.11
Charlson Comorbidity Index – Median (min-max)		7 (4-13)	7 (4-11)	0.97
Baseline delirium severity (Long CAM-S) – Median (min-max)		8 (3-15)	9 (4-14)	0.63

[figure not shown]
Legend: ADL: Activities of Daily Living; APACHE: Acute Physiology And Chronic Health Evaluation; CAM-S: Confusion Assessment Method Severity; SOC: Standard-of-care.

Figure 1: CONSORT Flow Diagram for non-pharmacologic interventions

Legend: SOC: Standard-of-care

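### Equality of the arms at baseline is inferred from non-significant tests in 50 vs 31 patients allocated by weekday; it was not shown, and four baseline measures leaning to acupuncture are missing from the Cox model

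*Combined protocol and SAP*

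**What the plan says.** METHODS, Statistical methods: after describing the baseline summaries, the text states "Next, we showed that our variables distribute equally between the two groups". For categorical variables the tool is a significance test: "we used the independent Chi-square test and Fisher exact test". The significance level is two-sided 0.05.

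RESULTS, Baseline patient data: "81 were recruited – 50 to the acupuncture arm and 31 to the SOC arm", followed by "Baseline sociodemographic and medical characteristics were similar in the two study arms as shown in Table 1".

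METHODS, Randomization: "Patients were randomized in two groups by convenience allocation according to acupuncturists' working days".

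Table 1 gives p-values only, with no standardized differences or intervals. The smallest p belongs to the row "Hearing and/or visual impairment", printed as "26 (52%) 22 (71%) 0.11".

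RESULTS, Primary endpoint: the adjusted Cox model has nine covariates: age, gender, APACHE-II, Charlson index, number of psychotropic drugs, mobilization, cognitive impairment, reason for admission and delirium type. The log-rank test, the NNT of 3 and the comparison of delirium-free days are reported without adjustment.

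**The concern.** A non-significant test says that the data are compatible with no difference. It does not say that the groups are equal, least of all with 31 patients in the smaller arm. Here the inference carries more weight than usual: allocation followed the weekday of diagnosis, so chance allocation does not protect balance, and measured balance is a main reason for reading the unadjusted results as treatment effects.

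Most of the ordered prognostic rows in Table 1 lean to acupuncture. Some of these variables are in the Cox model. Hearing/visual impairment, ADL, number of medications and baseline CAM-S are not, and no rule is given for leaving them out. At stake are the wording of the baseline claim, the reading of the unadjusted results, and the size and precision of the adjusted effect.

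**Working it through.** **Inputs.** All counts, medians and p-values are from Table 1; the arm sizes (50 and 31), the hazard ratio and the number censored are from the Results.

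**1. Reproducing the printed p-values.**
- Hearing/visual, 26/50 vs 22/31: Fisher exact p = 0.108, printed 0.11. Reproduced.
- Mobilization, (24, 15, 2, 9) vs (9, 15, 3, 4): chi-square p = 0.191, printed 0.19. Reproduced.
- Gender, prevalent delirium, IQCODE and delirium category also reproduce. Age gives 0.44 against 0.45, which is rounding.
- Reason for admission, (19, 9, 8, 3, 2, 9) vs (12, 9, 4, 3, 1, 2): chi-square 3.43 on 5 df, p = 0.63; a simulated exact test also gives 0.63. Printed 0.94. Not reproduced.
- Normal mobilization in the SOC arm is printed as 9 (19%). 9/31 = 29%. The column 9 + 15 + 3 + 4 = 31 and the reproduced p-value both confirm the count of 9, so the percentage is the error.

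**2. What p > 0.05 can rule out.** The standard error of a standardized difference is about √(1/50 + 1/31) = 0.229. With t(0.975, 79 df) = 1.99, significance needs 1.99 × 0.229 ≈ 0.46.

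**3. Standardized differences.** For proportions, SMD = (p1 − p2)/√[(p1q1 + p2q2)/2].
- Hearing/visual: (0.520 − 0.710)/√[(0.2496 + 0.2060)/2] = −0.190/0.477 = −0.40. The arm difference is 19 points, SE 0.108, 95% CI 40 points lower to 2 points higher with acupuncture.
- Normal mobilization, 24/50 vs 9/31: 0.40. Scored 0 to 3 over all four levels: means 0.92 vs 1.06, SMD 0.14 in absolute value.
- Normal cognition, 28/50 vs 12/31: 0.35. Scored 0 to 3 over all four levels: means 0.56 vs 0.71, SMD 0.22 in absolute value.
- Age: (84.0 − 85.3)/√[(7.8² + 6.7²)/2] = −0.18.
- Approximate absolute values implied by the printed p-values: APACHE-II 0.23, ADL 0.21, medications 0.20, CAM-S 0.11.

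**4. Power of the hearing/visual test.** If the true shares were 52% and 71%, power at 50 vs 31 is 39% (pooled variance under the null), 42% (unpooled) or 34% (the Fisher test that reproduces the printed p). A non-significant result is the likelier outcome on any of these.

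**5. Direction of the rows.**
- Leaning to acupuncture: age 84.0 vs 85.3, APACHE-II 9 vs 11, medications 8 vs 9, mobilization, IQCODE, ADL 4.5 vs 4, CAM-S 8 vs 9, and the yes/no hearing/visual row.
- Tied at the median: psychotropic drugs 1 vs 1, Charlson 7 vs 7.
- Running the other way: bedridden 18% vs 13%, subsyndromal delirium 6% vs 13%.
- Level: wheelchair or bedridden 22% vs 23%, moderate or severe dementia 10% vs 10%.

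**6. What the omission of hearing/visual impairment could do.** The documents give no effect of impairment on remission, so a range is assumed. Let impairment multiply the remission rate by h, independently of the other covariates. The bias factor is (0.48 + 0.52h)/(0.29 + 0.71h). The reported HR of 0.267 (0.098 to 0.726), inverted so that it reads as a remission ratio for acupuncture, is 3.75 (1.38 to 10.2).

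| h (assumed) | bias factor | ratio | lower limit |
|---|---|---|---|
| 0.5 | 1.15 | 3.27 | 1.20 |
| 0.25 | 1.30 | 2.87 | 1.06 |
| 0.1 | 1.47 | 2.54 | 0.94 |

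**7. Room in the model.** Coded by the printed levels, the nine covariates take 5 single terms + 3 (mobilization) + 3 (IQCODE) + 5 (reason) + 3 (delirium category) = 19, or 20 with arm. If only the 22 censored patients lacked remission, events number 81 − 22 = 59. The SOC median of 0 delirium-free days suggests fewer.

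**The case against.** The strongest reply is that nothing here shows imbalance beyond chance. With a chance standard deviation of about 0.23, a perfectly randomized trial of this size would exceed an SMD of 0.20 in about 38% of rows, so a small-difference flag tells one little. The largest values for mobilization and cognition depend on cutting an ordered scale at its top level; using all levels they fall to 0.14 and 0.22. Age, APACHE-II, mobilization and cognitive impairment are already in the Cox model. All of this stands.

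A reader might infer that the leaning rows form a consistent pattern that proves the arms differed. Eight of eight independent signs would give 2 × 0.5⁸ = 0.008, but the rows were picked by their direction, leave out two ties, and are likely to be correlated. Under an assumed common correlation of 0.2 to 0.5, all eight agree by chance in 6% to 22% of samples.

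The reply does not rescue the sentence in the methods. Compatibility with chance is not equality, and the Cox adjustment reaches neither the four omitted measures nor the unadjusted results.

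**Conclusion.** The claim of equality is unsupported and should go. The supported statement is that equality was not shown: most ordered measures lean to acupuncture, none significantly, and the tests could not have flagged standardized differences below about 0.46. The largest difference left out of the Cox model is hearing/visual impairment at 0.40; ADL, number of medications and baseline CAM-S are smaller.

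Two stronger readings are not supported. One is that calling the arms similar is false: the intervals are too wide to say so. The other is that the reported benefit is a product of baseline imbalance. Under the assumed range above, omitting hearing/visual impairment changes the size and precision of the adjusted ratio, and only an extreme assumed effect (h = 0.1) takes the lower limit below 1. That calculation covers this one variable and assumes that it is independent of the others.

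The two Table 1 errors are clerical. Correcting 19% to 29% narrows the printed gap, and 0.63 is still non-significant. Neither is evidence of bias.

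**What to change.** 1. Replace the equality sentence in Statistical methods and the similarity sentence in the Results with a description: which rows lean which way, which are tied, and that the trial is too small to establish equality.
2. Add a standardized difference for every Table 1 row, using all levels of the ordered variables.
3. Correct normal mobilization in the SOC arm to 9 (29%) and the reason-for-admission p to about 0.63.
4. Report, as a sensitivity analysis, the Cox arm effect with and without the omitted baseline variables, at least hearing/visual impairment and baseline CAM-S. State the number of events and the limit that it sets on the number of terms.
5. Label the log-rank, NNT and delirium-free-days results as unadjusted.

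The data are already collected, so the work is a few lines of output and one further model. The price is a wider interval, in a model that already has many terms for its events, and a less favourable baseline statement.

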**Treatment regimen:** The number of acupuncture treatments was set at up to five treatments in the one-week study period (treatments was not provided on weekends) or until the patient is delirium-free for 48 hours. Each session lasted 15-20 minutes.

**Other components of treatment:** Patients of acupuncture group also received SOC. Prior to the start of the study, a multicomponent protocol for delirium management was developed and implemented in internal medicine departments. This protocol was based on best literature evidence, current practice guidelines and the opinions of geriatric and psychiatric consultants, and included both pharmacological and non-pharmacologic interventions as published in a preceding manuscript. All clinicians working in the internal medicine departments were educated regarding the protocol and its use. This protocol was defined “SOC” for the study. Since the actual care of patients may differ according to clinical data and physician consideration, the use of psychotropic drugs (including antipsychotics) during hospitalization were documented and compared between the study arms. No other complementary medicine therapies other than acupuncture were added. Explanations were given to patients and their next-of-kin on potential benefits and side effects of acupuncture and treatment was administered only after they signed informed consent.

**Practitioner background:** The treatment was administered by seven acupuncturists with at least 5 years of clinical experience in a hospital setting.

**Control intervention:** In the control group, patients received SOC only.

**Outcomes:** All daily outcomes were collected daily for one week after randomization or until the patient was discharged from the hospital.

Primary outcome: Our primary endpoint was resolution of delirium during the 7 days of evaluation and was measured as time-to-first remission of delirium and number of delirium-free days, based on daily assessment of CAM scale.

Secondary outcomes:

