1. *Delirium severity:* Comparison of the sum of long CAM-severity (CAM-S) score from day 2 (before treatment in the second day of the study) until day 7 (last day of evaluation). The CAM-S tool includes 10 delirium-related items, the first one being rated on a 0-1 scale and the nine followings in a 0-2 scale for a total score ranging from 0-19. The items include the four CAM items described earlier in addition to disorientation, memory impairment, perceptual disturbances, psychomotor agitation, psychomotor retardation and altered sleep-wake cycle. The sum of long CAM-S score has been shown to best reflect both 30-day and 90-day post-hospital outcomes in patients with delirium.
2. *Number of days an antipsychotic drug was administered:* as mentioned in the daily study investigator chart review.
3. *Pain:* based on twice daily Visual Analogue Scale (VAS) scores for communicating patients and FRAAC (Facial expression, Respiration, Activity, Audibility, Cry and consolability) scores for non-communicating patients. Both scales are rated on a 0-10 score and are comparable in terms of pain severity. They were routinely recorded twice daily by registered nurses.
4. *Sleep quality:* as assessed by the tenth CAM-S item.
5. *Delirium complications:* daily evaluation of falls, pulling-out intravenous or urinary catheters, new or increase in pressure ulcers grade.
6. *Length of hospital stay*
7. *Functional status at discharge:* based on Katz ADL at discharge as evaluated by study investigators.
8. *Safety and adverse events:* A checklist with acupuncture adverse events based on the AcupAE questionnaire was adapted to our study. All adverse events were recorded and monitored daily. Acupuncture-associated adverse events were discussed by the research team and the family of patients and addressed accordingly. Severe adverse events requiring patient exclusion

from the clinical trial included pneumothorax, massive bleeding, or infection in the acupoint area requiring systemic antibiotic treatment.

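### Carrying the last CAM and CAM-S forward to day 7 after death counts days after a CAM-negative death as delirium-free in a primary measure

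*Combined protocol and SAP*

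**What the plan says.** - **Statistical methods** gives the rule: "Patients who died or were discharged before day 7 had all subsequent days counted as the last day of evaluation". The sentence goes on to apply it to CAM and CAM-S alike. Death and live discharge are covered together.
- **Outcomes, primary outcome** says that resolution of delirium is "measured as time-to-first remission of delirium and number of delirium-free days, based on daily assessment of CAM scale". Delirium-free days is therefore a primary measure and is built from the daily CAM to which the rule applies.
- **Secondary outcomes, item 1** sums the long CAM-S "from day 2 (before treatment in the second day of the study) until day 7 (last day of evaluation"), so the same filling-in feeds the severity outcome.
- **Results, Baseline patient data** reports for the acupuncture arm that "14 (28%) were censored (dead/discharged in the 7 days of follow-up), as compared with 8 (26%) in the SOC arm". It adds: "No difference in the baseline characteristics was noted between censored patients and patients completing the 7 days of follow-up". Deaths are not separated from discharges.
- **Results, Primary endpoint** gives the delirium-free days as "found in the acupuncture arm [median 5.5 (0-6)] as compared with the SOC arm [median 0 (0-6)], with p<0.001.

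The visible text has no separate rule for death, no definition requiring the patient to be alive, and no sensitivity analysis on this point. The flow diagram (Figure 1) is not visible and may give deaths.

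**The concern.** After a live discharge the patient still has a delirium status that nobody observed, and carrying the last value forward is a debatable assumption about it. After death there is no status to impute. Under the written rule, a patient who turns CAM-negative and then dies is credited with recovery on each later day. That places the worst outcome among the best scores.

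The trial asks about recovery from delirium in patients with a mean age of 84 to 85 years (Table 1), and the label used for the early leavers names death as one of the reasons. Credit given in the acupuncture arm inflates the between-arm difference in delirium-free days; credit given in the SOC arm shrinks it.

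The CAM-S sum has a related fault: the last score, low or high, is repeated for days on which the patient was not alive.

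**Working it through.** **Inputs.** Arms of 50 and 31; early leavers 14 and 8; delirium-free days with median 5.5 (range 0-6) and median 0 (range 0-6). All are from Results. The maximum of 6 fits a count over days 2 to 7.

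**1. Who the early leavers are.** 14/50 = 28% and 8/31 = 26%, as stated. 14 + 8 = 22, and 81 - 22 = 59 (36 acupuncture, 23 SOC). Results contrasts the censored patients with those completing 7 days, which suggests that the 22 are all the early leavers. If censored instead means leaving without remission, these 22 gain no credited days, and any CAM-negative leavers are simply not counted in the text. On either reading the number of CAM-negative deaths is not given.

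**2. Credit per death.** Credited days = 7 minus the last evaluation day. A last evaluation on day 6 gives 1; on day 2 it gives 5.
- Acupuncture mean: 1/50 = 0.02 to 5/50 = 0.10 days.
- SOC mean: 1/31 = 0.03 to 5/31 = 0.16 days.

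**3. One such death in each arm, credit removed.** Change in the mean difference (acupuncture minus SOC):
- lowest: -5/50 + 1/31 = -0.07 days
- highest: -1/50 + 5/31 = +0.14 days

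**4. The reported median.** With whole-day scores and a maximum of 6, a median of 5.5 requires an even number of patients with middle values 5 and 6, so exactly half scored 6. A patient scoring 6 who died after a last evaluation on day 2 to 6 has only 1 to 5 observed delirium-free days. Replacing one 6 by that value leaves 5 as the upper middle value. The lower one then lies between 1 and 5, so the median falls to between (5+1)/2 = 3 and (5+5)/2 = 5. Values below 5 need few other patients near 5. With other scores spread evenly over 0-5, or half of them at 5, the median becomes 5.

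**5. Significance (assumed data, not trial data).** Acupuncture: 25 patients at 6, one at 5, and 24 others (all 0; spread evenly over 0-5; or 12 at 5 and 12 at 0). SOC: 16 to 30 patients at 0, the rest all at 6 or mixed over 1-6. Data sets with a two-sided asymptotic Mann-Whitney p<0.001 were kept (59 in the main run). Up to 5 days were then taken from k acupuncture patients at 6, with SOC unchanged. Largest p:

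| k | largest p |
|---|---|
| 1 | 0.0011 |
| 3 | 0.0018 |
| 5 | 0.0028 |
| 10 | 0.0073 |
| 14 | 0.014 to 0.022 |

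The range at k=14 reflects different ways of arranging the mixed SOC scores. Fourteen is the full count of reported acupuncture leavers.

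**6. A harsher rule, for contrast.** Scoring a death as 0 days overall, which also discards days lived without delirium, gave p = 0.009 for 5 patients, 0.029 for 7 and 0.12 for 10 in one illustrative data set with the reported medians and ranges. The choice of rule for death can matter when deaths are many.

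**7. CAM-S.** The sum can range from 0 to 6 x 19 = 114. Each death repeats the last score 1 to 5 times. For scale only, a last score of 8 (the acupuncture baseline median) would add 8 to 40 points.

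**The case against.** The strongest reply is that no affected patient is shown. The harm needs someone who remitted and then died before day 7. The text reports none, early leaving was nearly equal between arms (28% and 26%), and Figure 1 may give the deaths. This stands: it limits the finding to the rule, with unknown size and direction.

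Second, time to first remission, which carries the log-rank test, the Cox model and the NNT, is untouched by this case, because a CAM-negative patient has already had the event. This also stands.

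Third, the severity categories in Results total 11+6+9+19 = 45 and 3+0+1+24 = 28, so 5 and 3 patients are absent from an outcome that the rule should have completed. Whether deaths are among them is unknown, so it cannot be assumed that the rule was actually applied to deaths in CAM-S. Results gives categories rather than sums, so the points in step 7 have no reported counterpart.

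Fourth, the results are known, and changing a primary measure now is post hoc. Scoring days after death as not delirium-free is one defensible choice among several. That argues for labelling the re-run clearly and showing it beside the reported analysis. It does not justify leaving the rule as it is: whatever the count of such deaths, the rule as written credits recovery to patients who have died.

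**Conclusion.** The concern holds. Followed as written, the plan scores days after a CAM-negative death as delirium-free in a primary measure and fills CAM-S after death in the same way. This should be fixed, but it is not shown to overturn the result.

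The mean effect is small for each death, while the acupuncture median is sensitive to a single patient among those scoring 6. Significance looks robust when only the credit after death is removed, even if all 14 reported acupuncture leavers were affected.

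This rests on three assumptions: that the rule means carrying the last value forward, which is its natural reading; that scores are whole days over days 2 to 7; and that the assumed data sets resemble the real ones.

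**What to change.** - Define the measure as days alive and delirium-free, with every day after death up to day 7 counted as not delirium-free. Keep the stated carry-forward for live discharges.
- Do not carry CAM-S past death. Do not simply stop the sum at death either, because fewer days give a lower, apparently better, sum. Analyse the sum with deaths handled separately, for example with a sensitivity analysis that ranks death worst.
- Report deaths and live discharges by arm with last CAM status, unless Figure 1 already does.
- Label the re-run as post hoc and show it next to the reported analysis.

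The cost is a sentence in the methods and a short re-run on data already held. If no patient died CAM-negative, saying so closes the point for delirium-free days. The downside is that the measure then combines survival with delirium, and the effect size may be less favourable.
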